7 DATA COLLECTION & MANAGEMENT

7.1 DATA COLLECTION

Data will be recorded at each visit (baseline and 4 weeks) on a paper CRF by the Researcher or delegated person and subsequently transcribed into the Data Management System database. The CRF will be used as source data but data relevant to a participant's general medical history will be recorded also in their medical casenotes. Data from the FMD and vascular stiffness will be entered into the Excel database as below.

7.2 DATA MANAGEMENT SYSTEM

Microsoft Excel will be used for data management and data management will be conducted as per TASC SOP48. The computer running EXCEL will be password protected and kept in a locked room. To prevent unauthorised access, computers will be accessible only to named individuals in the delegation log. Each individual will be given a password to log onto the computer. EXCEL will be used for the results, which are transcribed from paper CRFs. A spread sheet will be opened in EXCEL and will record only outcomes that are specified in the protocol. This spreadsheet will be saved on the University of Dundee secure server, backed up daily. A Disaster Recovery Plan is in place. No scripts or macros will be added to the EXCEL spreadsheet. The PI/Statistician responsible for data analysis will check the spreadsheet template for accuracy and format before any entry begins. Modification of the spreadsheet may occur until it is fit for purpose. The trial spreadsheet will be password protected and a copy of this password kept with the division secretary. Data entry will be a delegated responsibility. In order to be GCP compliant, data is entered the same day as visit or as soon as possible afterwards. The spreadsheet will be saved each time with date of entry thus an audit trail will be created on the EXCEL file. Subjects will be identified only by subject number(s) and age at consent. No participant identifiable information will be stored on the results spread sheet. Subjects will be cross checked with the Subject Log and/or Screening Log. As the paper CRF is completed, it will be checked for empty fields and fields outside of normal ranges. Data checking will include looking for fields outside of the subjects' normal ranges, which may lie within the normal expected general range. These will be highlighted by the Insert Comment facility available on EXCEL which also includes the name of the person highlighting the comment. All queries will be clarified with the PI or CI and any actions recorded. Any changes to the data in the CRF will be made a single line drawn through, initialled and dated. The original data will be clearly visible. The data on the EXCEL file will be always verifiable against the paper CRFs.

Verifying data

Data entry and checking will be undertaken by a single entry with a second look or a Single entry with a second individual reading aloud. The data entry and checking process will be decided according to risk. Data that is recorded in the CRF that is not source document in itself will be consistent with the source documents or the discrepancies explained. Checks will be made on all missing values and values out with normal or expected ranges and that values entered are of the correct type: i.e. numerical instead of text. Logical checks will be performed to ensure consistent reporting between relevant fields and that there are no differences between fields. Data checking will continue until all missing data and/or inconsistent values have been corrected or clarified. When data checking is complete, with no outstanding data queries, the database will be locked, using the Protect Worksheet function of EXCEL, as FINAL RESULTS. The EXCEL spreadsheet will remain archived on the Dundee University secure server for 10 years for the retention of essential documents, thereafter it will be deleted.

8 STATISTICS AND DATA ANALYSIS

8.1 SAMPLE SIZE CALCULATION

The primary endpoint measurement is change in brachial artery FMD, which is expressed as the maximum FMD percentage change from baseline. Based on our existing data for this measure (mean response 7.8%, SD=3.5%), and assuming mean FMD reductions of 2%, 1% and 0% in the EC-Nicotine-free, EC-Nicotine, and TC groups respectively with a SD of the change in FMD =3.0% (based on our previous study³¹), and a using a sample size calculation using Linear Contrast Tests³⁷ a sample size of 36 subjects in each group will have 80% power to detect an improvement in FMD of 2.0% and 1.0% in the EC-nicotine-free and EC-nicotine groups respectively compared to the TC group at 5% significance. Assuming 10%, 15%, and 20% drop-out rates in the TC, EC-nicotine & EC-nicotine-free groups respectively, we will require 135 completed subjects. **All drop-outs will be replaced to achieve 36 completed subjects in each group.**

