SUSAR	Suspected Unexpected Serious Adverse Reaction
CNORIS	Clinical Negligence and Other Risks Scheme
SmPC	Summary of Product Characteristics
NRES	National Research Ethics Service
REC	Research Ethics Committee
MHRA	Medicines and Healthcare Products Regulatory Agency

SUMMARY

Electronic cigarettes (EC) are gaining popularity as an alternative to Traditional Cigarettes (TC). Despite not containing all the harmful substances seen in TC, EC are known to contain impurities that may have a detrimental impact on human health. The effects of ECs compared with TC on vascular function, inflammation and oxidative stress are unknown. It is increasingly recognised that nicotine itself has significant atherothrombotic effects. Therefore, clinicians are unable to confidently recommend ECs as a less risky alternative to TC.

Hypothesis: Endothelial function will be improved on EC compared to TC when measured by flow mediated dilatation (FMD).

Aims: To assess the effects of EC-nicotine and EC-nicotine free on endothelial function as compared to TC.

Design: Single centre, 2-cohort parallel group, randomised controlled trial. with a comparator TC arm

Population: ≥ 18 years old, current TC smokers. Excluding those with cardiovascular disease (hypertension allowed).

Interventions: 2 groups will be randomised to either EC-nicotine or EC-nicotine free for 4 weeks. 1 group of TC smokers will be recruited as a comparator arm

Outcomes: the primary outcome is the change in endothelial stiffness as measured by Flow Medicated Dilatation between the TC and EC-nicotine free groups. Secondary outcomes are change in endothelial stiffness between EC-nicotine free and EC-nicotine groups and change in oxidative stress between all 3 groups.

Assessments: performed at baseline and 4 weeks.

Samples size: 135 participants randomised to 2 groups EC-nicotine (n=45) and EC-nicotine free (n=45) plus a comparator arm of TC (n=45), will have a 80% power to detect an improvement in FMD of 2.0% and 1.0% in the EC-nicotine free and EC-nicotine groups respectively compared to the TC group at 5% significance. This allows for a 10%, 15%, and 20% drop-out rates in the TC, EC-nicotine & EC-nicotine-free groups respectively.

Statistical Analysis: Change in outcome measures between interventions will be assessed by a linear contrast test, and a linear regression including the baseline FMD level and experimental group as covariates.

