2 STUDY OBJECTIVES & OUTCOMES

Table 1: Primary Objectives and Outcome Measures

Primary Objective	Outcome Measure	Timepoints measured
To determine the effect of EC-nicotine free on vascular function as compare to TC.	Change in FMD between the TC group and the EC-nicotine free groups	0 and 4 weeks

Table 2: Secondary Objectives and Outcome Measures

[figure not shown]
Secondary Objectives	Outcome Measures	Timepoints measured
To compare the effects of EC-nicotine vs EC-nicotine free on vascular function.	Change in FMD between EC-nicotine and EC-nicotine free groups	0 and 4 weeks
To compare the effects of EC-nicotine free vs TC on vascular function.	Change in Pulse Wave Velocity between the TC group and the EC-nicotine free groups. Change in Augmentation Index@75bpm between the TC group and the EC-nicotine free groups	0 and 4 weeks
To compare the effects of TC vs EC vs EC nicotine free on oxidative stress.	Change in total F2-Isoprostanes between the TC and EC groups	0 and 4 weeks

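### The 80% power applies to one contrast (EC-nicotine-free vs TC) but is worded as also covering a 1.0-point EC-nicotine effect (about 29%), and the protocol and SAP 4.1 name different primary comparisons

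*Protocol*

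**What the plan says.** **Power.** Protocol 8.1 assumes mean FMD changes of 2, 1 and 0 points in the EC-nicotine-free, EC-nicotine and TC groups and an SD of change of 3.0. It arrives at 36 per group "using a sample size calculation using Linear Contrast Tests" and states that this number "will have 80% power to detect an improvement in FMD of 2.0% and 1.0% in the EC-nicotine-free and EC-nicotine groups", respectively, compared with TC at 5% significance. SAP 5.1 repeats the statement. The protocol Summary makes the same claim for 45 per group before dropout: the sample "will have a 80% power to detect an improvement in FMD of 2.0% and 1.0% in the EC-nicotine free and EC-nicotine groups".

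**Primary comparison.** The protocol Summary says "the primary outcome is the change in endothelial stiffness as measured by Flow Medicated Dilatation between the TC and EC-nicotine free groups". Protocol Table 1 agrees: "Change in FMD between the TC group and the EC-nicotine free groups". The only FMD entry in Protocol Table 2 is "Change in FMD between EC-nicotine and EC-nicotine free groups". SAP 4.1, by contrast, defines the primary outcome as the change in FMD between TC and both EC groups.

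**Aim and analysis.** The protocol's stated aim is broader than its Table 1: "To assess the effects of EC-nicotine and EC-nicotine free on endothelial function as compared to TC". SAP 8 analyses FMD by a linear contrast test and by a multiple regression of 4-week FMD on baseline, group and the minimisation variables. It does not say which result decides. SAP 6.1 holds that the statistician need not be blinded because the SAP will be followed.

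**The concern.** Taken at its word, the power sentence promises 80% for two differences from TC, one half the size of the other, with equal groups and a common SD. Both cannot have 80%. A reader who accepts the sentence would treat a null EC-nicotine vs TC result as informative when the trial had little chance of finding the assumed effect.

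The disagreement over the primary comparison matters more. EC-nicotine vs TC on FMD is part of the protocol's aim, is absent from both of its outcome tables, and is primary in the SAP. SAP 4.1 can be read as two pairwise tests, as pooled EC vs TC, or as one three-group trend, and these readings differ in power and error rate. Following the SAP protects an analysis by an unblinded statistician only if the SAP names one primary comparison and the protocol agrees with it.

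**Working it through.** **Inputs** (Protocol 8.1 and SAP 5.1): n = 36 per group, SD of change 3.0, mean changes 0 / 1 / 2 for TC / EC-nicotine / EC-nicotine-free, 5% significance. Contrast weights and sidedness are not stated; I take (-1, 0, +1) and two-sided. The text calls the assumed changes both reductions and improvements; only their size affects power.

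**Reproducing the 80%.** The noncentrality is the difference divided by its standard error, and power comes from the noncentral t with 3 × 36 − 3 = 105 df.
- Contrast: (−1)(0) + (0)(1) + (1)(2) = 2.0 points.
- Standard error: 3.0 × √(2/36) = 0.707.
- Noncentrality: 2.0 / 0.707 = 2.828, giving power **80.0%**. With 35 per group it is 78.9%, so 36 is the smallest adequate number.
- Other tests do not give 80% at n = 36: the overall F test gives 70.4% and a one-sided 5% contrast 87.8%.

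Because EC-nicotine has weight zero, the result is 80.0% whether its true effect is 0, 1 or 2 points.

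**EC-nicotine vs TC at 1.0 point**, two-sided 5%:

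| Completers | Noncentrality | df | Power |
|---|---|---|---|
| 36 per group | 1.0 / 0.707 = 1.414 | 105 | 28.9% |
| 40 TC, 38 EC-nicotine, 36 EC-nicotine-free (45 per arm less 10%, 15%, 20%) | 1.0 / [3√(1/40 + 1/38)] = 1.47 | 111 | 30.8% |
| 45 per group, no dropout | 1.0 / [3√(2/45)] = 1.58 | 132 | 34.8% |

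- The expected 95% CI half-width at n = 36 is 1.983 × 0.707 = 1.40 points, more than the effect itself.
- For 80% power about 142 per arm would be needed (141 gives 79.7%, 142 gives 80.0%).

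**With baseline adjustment.** The residual SD is s₁√(1 − r²), where r = (s₀² + s₁² − 3.0²) / (2s₀s₁). The baseline SD s₀ is taken as the 3.5 in Protocol 8.1. The 4-week SD s₁ is not given, so I show a range.

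| Assumed 4-week SD | Power, 1.0 point | Power, 2.0 points |
|---|---|---|
| 3.0 | 40.7% | 93.2% |
| 3.5 | 34.1% | 87.3% |
| 4.0 | 30.4% | 82.5% |
| 4.5 | 28.9% | 80.1% |

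**The readings of SAP 4.1**, unadjusted, n = 36:
- *Two pairwise tests against TC:* 80% and 29%. Both are significant in 27% of simulated trials under 0 / 1 / 2. With each tested at 5%, the familywise error is 9.0% when there is no effect (2 million simulated draws sharing the TC arm).
- *Pooled EC vs TC:* weights (−1, ½, ½), difference (1 + 2)/2 = 1.5 points, standard error 3.0 × √(1.5/36) = 0.612, noncentrality 2.45, power 68%.
- *One linear trend:* 80%, a single 5% test, no inflation.

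**The case against.** The best defence is that the power sentence describes one trend test. It lists the three means, names the linear contrast method, and then restates the pattern, so that *respectively* assigns effects to arms rather than a separate 80% to each pair. No stated number would change. Protocol 8.2 and SAP 8 both specify a linear contrast, which with the inferred weights is exactly Table 1's comparison, and nothing in the SAP sets out two co-primary tests or a pooled EC arm. Protocol 3.1 does mention TC vs EC as a purpose of the three arms. FMD is read by a blinded operator. Finally, 29% is an unadjusted figure, whereas the planned model adjusts for baseline.

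Much of this is fair but does not remove the point.
- The trend may well be what was intended, and SAP 8 favours it. But the sentence says what will be detected in each group against TC, and that is untrue for 1.0 point.
- The 27% and 9% apply only to the pairwise reading, and the 68% only to the pooled one. No text settles which reading holds.
- Protocol 3.1 repeats the aim without giving EC-nicotine vs TC a place in the outcome tables.
- A blinded operator protects the measurement, not the choice of primary comparison.
- The 29% is on the same change-score basis as the plan's 80%. Adjustment could raise it to 41% over the range shown, and to 52% if the 4-week SD were as low as 2.5. None of these is near 80%.

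**Conclusion.** The point holds. The sample size of 36 per group is correct, and the protocol's own primary comparison keeps its 80%. The stated power is wrong as worded for the 1.0-point EC-nicotine effect: about 29% on the plan's assumptions, so a true effect of that size would be missed about 7 times in 10. Separately, the protocol and SAP 4.1 name different primary comparisons, and no text reconciles them or controls the error rate if both stand.

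The 80.0% rests on the inferred weights and a two-sided test, which together reproduce the plan's figure. The low power for EC-nicotine vs TC does not depend on the weights, and even a one-sided test gives only 40 to 41%. The conflict over the primary comparison rests on the text alone and should be resolved before analysis.

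**What to change.** 1. **Power statement** (protocol Summary, Protocol 8.1, SAP 5.1). Replace with wording such as: *36 completers per group give 80% power (two-sided 5%) for a single linear contrast with weights -1, 0, +1 for TC, EC-nicotine and EC-nicotine-free, that is, for a 2.0-point EC-nicotine-free vs TC difference in the change in FMD. A 1.0-point EC-nicotine vs TC difference on its own has about 29% power, before any gain from baseline adjustment.* Confirm that the weights and sidedness are those used.
2. **Primary comparison.** Align SAP 4.1 with Protocol Table 1 so that one comparison is named. EC-nicotine-free vs TC matches the sizing. EC-nicotine vs TC on FMD would then enter the outcome list as a non-primary comparison, reported with a confidence interval. If both stay primary, state how the 5% error rate is controlled.
3. **SAP 8.** Confirm that the contrast is computed within the baseline-adjusted model, as SAP 5.2 implies, so that there is one primary p-value.

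The cost is wording in the two documents and no extra participants. What is given up is the claim that EC-nicotine vs TC is adequately powered; it becomes an estimate with a wide interval.

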8.2 PROPOSED ANALYSES

Descriptive statistics in the form of means and standard deviations for continuous variables and percentages and denominators will be tabulated for baseline and at each visit. The dependent variable will be assessed for approximation to a normal distribution and transformed if necessary. Pre-specified subgroup analyses will be completed by fitting the appropriate interaction term in the regression model and if significant outcomes will be presented separately by level of subgroup. The FMD response relationship will be assessed by a linear contrast test, and a linear regression including the baseline FMD level and experimental group as covariates.

The statistical analysis will be carried out in accordance to TASC SOP “Statistical Analysis Plans for Clinical Trials of Investigational Medicinal Products” by the study team statistician.

8.3 MISSING DATA

The primary analysis will be on a per protocol basis. **We will perform an intention to treat analysis as a secondary analysis.**..The extent of missing data will be examined

and the reason for drop-out ascertained. Multiple imputation will be used to impute missing values if the assumptions for missing at random (MAR) data are met.

8.4 TRANSFER OF DATA

Transfer of data out with the study site will not occur.

9 SERIOUS ADVERSE EVENTS

9.1 RECORDING AND REPORTING SAEs

Adverse events will not be recorded in this non-CTIMP study unless they are deemed as serious (SAE). All SAE will be recorded in a SAE Log.

A serious adverse event (SAE) is defined as an untoward occurrence that:

- results in death;
- is life-threatening;
- requires hospitalisation or prolongation of existing hospitalisation;
- results in persistent or significant disability or incapacity;
- consists of a congenital anomaly or birth defect;
- or is otherwise considered medically significant by the investigator

Note: Hospitalisations for treatment planned prior to randomisation and hospitalisation for elective treatment of a pre-existing condition will not be considered as an SAE. However any serious adverse events occurring during such hospitalisation will be recorded.

An SAE occurring to a research participant will be reported to the main REC and Sponsor where in the opinion of the Chief Investigator (CI) the event was:

Related – that is, it resulted from administration of any of the research procedures, **and**

Unexpected – that is, the type of event is not listed in the protocol as an expected occurrence.

Other SAE will not be reported.

SAEs will be reported as per HRA guidelines to the REC and Sponsor:

	Who	When	How	To whom
SAE	Chief Investigator (CI)	Within 15 days of the CI becoming aware of the event	SAE report form for non-CTIMPs	Main REC for the trial. Sponsor
Urgent safety measures	Chief Investigator (CI) or sponsor Or exceptionally by local principal investigator (PI)	(i) Immediately (ii) Within 3 days	(i) By telephone (ii) Notice in writing setting out the reasons for urgent safety measures and the plan for further action	Main REC, trial REC co-ordinator will acknowledge within 30 days Sponsor

10 TRIAL MANAGEMENT AND OVERSIGHT ARRANGEMENTS

10.1 TRIAL MANAGEMENT GROUP

The trial will be co-ordinated by a Trial Management Group, consisting of the grant holders, Trial Manager, Research Nurse and Senior Trial Manager (TCTU). The Trial Management Group will also act as the Trial Steering Committee (TSC). A Data Monitoring Committee is not considered necessary as this is a relatively small study involving a marketed intervention, this role will be undertaken by the TMG also.

10.2 TRIAL/STUDY MANAGEMENT

A Trial Coordinator will oversee the study and will be accountable to the CI. The Trial Coordinator or Research Nurse will be responsible for checking the CRFs for completeness, plausibility and consistency. However, this remains the overall responsibility of the CI. Any queries will be resolved by the CI or delegated member of the study team.

A study-specific Delegation Log will be prepared, detailing the responsibilities of each member of staff working on the study.

10.3 INSPECTION OF RECORDS

The CI, PIs and all institutions involved in the study will permit study related monitoring, audits, and REC review. The CI agrees to allow the Sponsor or, representatives of the Sponsor, direct access to all study records and source documentation.

11 GOOD CLINICAL PRACTICE

11.1 ETHICAL CONDUCT OF THE STUDY

The study will be conducted in accordance with the principles of good clinical practice (GCP).

In addition to Sponsorship approval, a favourable ethical opinion will be obtained from an appropriate REC. Authorisation from an appropriate competent authority(s) and appropriate NHS R&D permissions(s) will be obtained prior to commencement of the study.

11.1.1 Confidentiality

All laboratory specimens, evaluation forms, reports, and other records will be identified in a manner designed to maintain participant confidentiality. All records will be kept in a secure storage area with limited access to study staff only. Clinical information will not be released without the written permission of the participant, except as necessary for monitoring and auditing by the Sponsor, its designee or Regulatory Authorities. The CI and study staff involved with this study will not disclose or use for any purpose other than performance of the study, any data, record, or other unpublished, confidential information disclosed to those individuals for the purpose of the study. Prior written agreement from the Sponsor or its designee will be obtained for the disclosure of any said confidential information to other parties.

11.1.2 Data Protection

The CI and study staff involved with this study will comply with the requirements of the Data Protection Act 1998 with regard to the collection, storage, processing and disclosure of personal information and will uphold the Act's core principles. The CI and study staff will also adhere, if appropriate, to the current version of the NHS Scotland Code of Practice on Protecting Patient Confidentiality. Access to collated participant data will be restricted to the CI and appropriate study staff.

Computers used to collate the data will have limited access measures via user names and passwords.

Published results will not contain any personal data that could allow identification of individual participants.

11.1.3 Insurance and Indemnity

The University of Dundee and Tayside Health Board are Co-Sponsoring the study.

Insurance –The University of Dundee will obtain and hold a policy of Public Liability Insurance for legal liabilities arising from the study.

Tayside Health Board will maintain its membership of the Clinical Negligence and Other Risks Insurance Scheme (“CNORIS”) which covers the legal liability of Tayside in relation to the study.

Where the study involves University of Dundee staff undertaking clinical research on NHS patients, such staff will hold honorary contracts with Tayside Health Board which means they will have cover under Tayside's membership of the CNORIS scheme.

Indemnity The Co-Sponsors do not provide study participants with indemnity in relation to participation in the Study but have insurance for legal liability as described above.

